12.4 Multiple Comparisons / Multiplicity

No hypothesis testing is planned.

12.5 Examination of Subgroups

Summaries for below subgroups will be tabulated for the change from Baseline in the HAMD-17 total score, the SDS mean score, the CGI-S score, the CSFQ-14 score, and the KSS score:

- age group (18-40 years and >40 years)
- sex (male and female)
- background antidepressant type (SSRI [citalopram, escitalopram, paroxetine, fluoxetine, or sertraline] and SNRI [duloxetine, venlafaxine, desvenlafaxine, or venlafaxine XR])

13 METHODS OF EFFICACY ANALYSES

Descriptive statistics for all efficacy endpoints listed in [Section 12.1](#) including treatment responder and remission rates will be tabulated by the double-blind treatment group in the antecedent studies at scheduled timepoints. The summaries of the change from Baseline results will be presented in two ways (main analysis and exploratory analysis) as specified in [Section 5.1](#).

14 SAFETY ANALYSES

The safety summaries will be presented for the Safety Analysis Set using descriptive statistics. Safety variables include AEs, clinical laboratory variables, vital signs, body weight, BMI, physical examinations, ECG, C-SSRS, ESRS-A, and sexual dysfunction defined as a CSFQ-14 total score of ≤ 47 for men and ≤ 41 for women. Safety variables will also be summarized by the double-blind treatment group in the antecedent studies. For each continuous measure in clinical laboratory variables, vital signs, and electrocardiogram, change from Baseline results will be presented in two ways (main analysis and exploratory analysis) as specified in Section 5.1.

14.1 Adverse Events

An AE is considered as treatment-emergent adverse event (TEAE) if it started on or after the open-label first study dose date and no later than the open-label last study dose date + 30 days.

The event counts and the number and percentage of subjects reporting TEAEs will be tabulated by SOC and preferred term; and, by SOC, preferred term, and maximum severity. If more than 1 AE occurs with the same preferred term for the same subject, the subject will be counted only once for that preferred term using the most severe occurrence for the summarization by severity. In addition, the event counts and the number and percentage of subjects with TEAEs classified by the Investigators as related to the study drug, with most

frequently reported TEAEs (preferred terms reported by $\geq 5\%$ of subjects in the Safety Analysis Set), with treatment-emergent serious AEs (TESAEs), with fatal AEs (i.e. events that cause death), and with TEAEs leading to discontinuation of study drug will be summarized by SOC and preferred term. The display in these tables will be sorted alphabetically by SOC and then by descending subject frequency for the preferred terms (based on counts in the Safety Analysis set) within each SOC.

The relationship of selected AEs to COVID-19 will be assessed as detailed in the GSD. TEAEs tabulated by SOC and preferred term will be presented three ways: all TEAE, COVID-19 related TEAE, and not COVID-19 related TEAE.

The event counts and the number and percentage of subjects with any TEAEs will also be tabulated by preferred term without SOCs. The display in this table will be sorted by descending subject frequency based on counts in the Safety Analysis set.

An AE listing by subject will display all events, including those which are not treatment-emergent, and will include the verbatim term in addition to the MedDRA SOC and preferred term. This listing will also include all relevant eCRF data associated with the event: e.g. date of onset, date resolved, date of the open-label first dose, date of the open-label last dose, dose level at AE onset, severity, frequency, outcome, relationship to study drug, action taken with study drug, and required therapy. When a date is presented, the study day associated with the date will also be displayed. Separate listings will be presented for subjects with SAEs, subjects with AEs leading to discontinuation and subjects who died (if any), and subjects with all COVID-19 related AEs.

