- c Subject consent for the present study **must be** obtained for entry into the present study prior to the final procedures being performed at the end of treatment (EOT) visit in the antecedent study, Study ACP-103-054 or Study ACP-103-059. Data from the EOT visit procedures of Study ACP-103-054 and Study ACP-103-059 will be carried over as baseline information in the present study, as applicable.
- d Relevant information collected from Study ACP-103-054 and Study ACP-103-059 will be rolled over to the present study; any updates to this information should be collected during the Baseline visit of the present study.
- e A single 12-lead ECG can be performed any time before blood sampling or at least 30 minutes after blood sampling during clinic visits. ECGs should be completed with the subject in a supine position after 5 minutes of rest. In the US and UK, a 6-lead ECG device will be given to subjects in order to perform ECGs on themselves at home when they cannot go to the clinic and site staff cannot go to their home. This should be done in discussion with the Medical Monitor. When an ECG is performed outside of the investigator site, this should be documented in the source record.
- f To include hematology, serum chemistry, prolactin levels, and urinalysis.
- g A urine pregnancy test should be performed for female study subjects of childbearing potential. If urine cannot be obtained in women of childbearing potential, a serum pregnancy test should be done in its place.
- h The HAMD-17 is to be the first scale completed at each visit.
- i All ongoing AEs from Study ACP-103-054 and Study ACP-103-059 will be carried over after informed consent has been obtained for the present study and recorded from Baseline for the present study until resolution or the follow-up safety assessment. An AE occurring after the completion of procedures at the EOT visit in Study ACP-103-054 or Study ACP-103-059 will be recorded as an AE in the present study.
- j Study drug will be dispensed to the subject to take home at the Baseline visit. The subject will be instructed to take the first dose of study drug on the following day.

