### **4.1 Inclusion Criteria**

A subject must meet all of the following inclusion criteria to be eligible for participation in the study.

1. Completed the antecedent study, Study ACP-103-054 or Study ACP-103-059
2. May benefit from longer term therapy with open-label pimavanserin treatment in the judgment of the Investigator
3. Is willing and able to provide informed consent. Consent for the present study **must be** obtained prior to the procedures being performed at the Week 6/EOT visit of Study ACP-103-054 or Study ACP-103-059

4. Is capable of communicating with the site personnel, able to complete subject-reported outcome measures and can be reliably rated on assessment scales (in the opinion of the Investigator)
5. If the subject is female, she must not be pregnant or breastfeeding. She must also be of non-childbearing potential (defined as either surgically sterilized or at least 1 year postmenopausal) OR must agree to use TWO clinically acceptable methods of contraception during the study and 1 month following completion of the study.

Acceptable methods of contraception include the following:

- a. A barrier method (condom, diaphragm, or cervical cap) with spermicide
- b. Hormonal contraception, including oral, injectable, transdermal, or implantable methods
- c. Intrauterine device (IUD)

Only one of the two clinically acceptable methods can be a hormonal method.

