#### 7.2.2.1 Duration

The start and stop dates for AEs will be recorded using the following criteria:

- **Start:** Date of the first episode of the AE or date of significant sustained worsening in severity
- **Stop:** Date when AE either ceased permanently or changed in severity

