#### **7.3 Time Period and Frequency for Event Assessment and Follow-up**

Adverse events with an onset before the first dose of open-label pimavanserin in the present study will be recorded as an AE in the antecedent study. All ongoing AEs from Study ACP-103-054 and Study ACP-103-059 will be carried over after informed consent has been obtained for the present study and recorded from Baseline for the present study until resolution or the follow-up safety assessment. An adverse event occurring after the first dose of open-label pimavanserin in the present study will be recorded as an AE in the present study. Adverse events for the present study will be recorded from the time of first dose of open-label pimavanserin through the study safety follow-up period.

All AEs must be either resolved or stable at the end of the study safety follow-up period of the present study. If ongoing at the end of the study safety follow-up period, the subject should be referred for appropriate treatment.

In the event that a subject discontinues and has an ongoing AE at the time of discontinuation ([Section 4.4.1](#)) or is withdrawn from the study because of an AE, the subject should be followed and treated by the Investigator until the AE has resolved, stabilized, or a new chronic baseline has been established.

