#### **9.5.1 Primary Analyses**

All AEs will be classified into standard terminology using the Medical Dictionary for Regulatory Activities (MedDRA). All AEs will be listed and TEAEs will be summarized by system organ class and preferred term. A TEAE is defined as an AE that started after the first administration of study drug and no later than the last administration of study drug plus 30 days. Summaries by maximum severity and by relationship to study drug will also be provided. Serious TEAEs, fatal AEs, and TEAEs leading to discontinuation will also be summarized. The relationship of selected AEs to COVID-19 will also be assessed and COVID-19 related TEAEs will be tabulated.

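### The by-event discontinuation table counts only TEAEs, so a carried-over adverse event that does not worsen but leads to withdrawal of open-label drug is not in it

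*SAP*

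**What the plan says.** The SAP defines treatment emergence by onset alone (14.1): "An AE is considered as treatment-emergent adverse event (TEAE) if it started on or after the open-label first study dose date", and no later than 30 days after the last open-label dose. The definition does not mention worsening of a pre-existing event. The discontinuation table in the same section covers TEAEs only: "and with TEAEs leading to discontinuation of study drug will be summarized by SOC and preferred term". Protocol 9.5.1 has the same scope: "Serious TEAEs, fatal AEs, and TEAEs leading to discontinuation will also be summarized". In both documents fatal events carry no TEAE restriction, although they stand in the same sentence.

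Events still ongoing at the end of the antecedent study are followed here. Table S-1, footnote i, and Protocol 7.3 both say: "All ongoing AEs from Study ACP-103-054 and Study ACP-103-059 will be carried over after informed consent has been obtained for the present study". On attribution, Protocol 7.3 says that an event with "onset before the first dose of open-label pimavanserin in the present study will be recorded as an AE in the antecedent study". Protocol 7.2.2.1 defines the start of an event as "Date of the first episode of the AE or date of significant sustained worsening in severity", and a change in severity ends the earlier record. Inclusion criterion 1 (Protocol 4.1) is "Completed the antecedent study, Study ACP-103-054 or Study ACP-103-059".

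The SAP also plans a disposition table by reason for discontinuation (Section 6). SAP 14.1 adds a full adverse event listing that includes events that are not treatment-emergent, and a separate listing of subjects with adverse events leading to discontinuation. That second listing is not limited to TEAEs.

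**The concern.** The primary objective is long-term safety and tolerability, and the table of events that made subjects stop drug is one of its main summaries. In a rollover study some subjects arrive with an event already under way. If such an event persists at the same severity until open-label drug is withdrawn, the stop happened in this study and on this study's drug, yet the onset rule removes the event from the table. The table then understates how many subjects stopped drug because of an adverse event, and it does not show which events were responsible.

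The plan is also uneven in scope. Fatal events and the discontinuation listing are free of the TEAE limit, while the discontinuation table is not. Table and listing can therefore show different subjects, and no reconciliation is described.

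**Working it through.** The plan states no figure on this point, so there is none to reproduce. The check traces an event that leads to withdrawal of open-label drug through the rules.

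**Inputs.** TEAE definition and table scope: SAP 14.1 and Protocol 9.5.1. Start and stop rules: Protocol 7.2.2.1. Carry-over and attribution: Protocol 7.3 and Table S-1, footnote i. Unclear dates: SAP 5.4.3. Disposition: SAP 6, with the reasons in Protocol 4.4. Entry: Protocol 4.1. Planned number: SAP 3.5.

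**Trace.**

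| Event leading to withdrawal | TEAE? | By-event discontinuation table | Discontinuation listing |
|---|---|---|---|
| Onset on or after the first open-label dose date | Yes | Included | Included |
| Carried over, significant sustained worsening after the first open-label dose | Yes, through a new start date | Included, if the site opens a new record | Included |
| Carried over, order of onset unclear from missing or partial dates | Yes, by the default in SAP 5.4.3 | Included | Included |
| Carried over, known earlier onset, no significant sustained worsening | No | **Not included** | Included |

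In all four rows disposition counts the subject if an adverse event is the recorded reason. Disposition does not name the event, and its planned breakdown is by antecedent study, not by prior treatment. The listing names the event but gives no incidence.

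**The antecedent study.** Entry requires completion of that study. An event that later stopped open-label drug is therefore presumably not a discontinuation event there either. This is an inference from inclusion criterion 1, because the antecedent plans are not among the documents.

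**Size.** If k subjects stop for an event in the last row, the table understates the percentage by k/N.

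- Planned N = 420: 1/420 = 0.24 percentage points per subject.
- N = 200, an assumed value chosen only because SAP 3.5 says the number will fall below the estimate: 1/200 = 0.50 percentage points per subject.

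The documents give no value for k. Within a single prior-treatment column the denominator is smaller than N, so each subject weighs more.

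**Prior-treatment columns.** Safety variables are also summarised by antecedent double-blind treatment (SAP 5.1 and 14). Subjects from the pimavanserin arm had their first exposure before open-label Day 1, so early drug-related events may fall on the excluded side of the onset rule. Subjects from the placebo arm have their first exposure after it. They can carry over ongoing events too, and those are excluded in the same way.

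**A related passage to reconcile.** Footnote i of Table S-1 assigns an event arising after the antecedent end-of-treatment procedures to the present study. Protocol 7.3 assigns an event arising before the first open-label dose to the antecedent study. The first dose is due the day after Baseline. An event with onset before the first-dose date fails the SAP's TEAE definition under either rule.

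**The case against.** The strongest reply is that the plan already identifies these subjects. The discontinuation listing is not limited to TEAEs. The full listing shows onset, first open-label dose date, preferred term and action taken. Disposition counts the stop whatever the onset date. The study is descriptive, protocol and SAP agree on the table's scope, and the table specifications sit in a separate document that is not available. Exclusion criterion 1 removes subjects judged inappropriate because of adverse events in the antecedent study, and inclusion criterion 2 asks that the subject may benefit from longer treatment, so the group is probably small. All of this stands. It limits the gap to one table and one kind of event, but it does not put that event in the table.

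A reader might infer more than the documents support:

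- *That every carried-over event leading to withdrawal is lost.* Events with significant sustained worsening get a new start date under Protocol 7.2.2.1, and unclear onsets default to treatment-emergent.
- *That the table must favour continued pimavanserin.* Both arms can carry events over, and nothing in the documents gives the net difference.
- *That a large share of stops is missed.* If 21 of 420 subjects (5%) stopped for a TEAE and a further 4 to 13 (about 1% to 3%) for a carried-over event, the share missed would be 4/25 = 16% to 13/34 = 38%. Both rates are assumptions, and the upper end needs carried-over stops equal to 13/21 = 62% of TEAE stops.
- *That the table and disposition ought to agree exactly.* Disposition records reasons for leaving the study, while the table concerns stopping study drug. Some difference can be legitimate.

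**Conclusion.** The gap is real and narrow. As written, an adverse event carried over with a known onset before the first open-label dose and no significant sustained worsening, which leads to withdrawal of open-label drug, is absent from the only discontinuation table by SOC and preferred term. It remains in the listing, and the subject remains in disposition if an adverse event is the recorded reason. What is lost is its incidence by event and by prior treatment.

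The number affected cannot be derived from the documents, and neither the share of stops missed nor the direction of any imbalance between columns is established. That the event is also missing from the antecedent study's discontinuation table is an inference. That worsened events are counted depends on sites opening a new record, because the SAP's definition does not mention worsening. The change is worth making as a cheap improvement to a key tolerability table; the gap does not invalidate the safety analysis.

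**What to change.** In SAP 14.1, with Protocol 9.5.1 worded to match:

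1. Tabulate by SOC and preferred term all adverse events with the action *Drug withdrawn* in the open-label period, whatever their onset. Give separate sub-rows for TEAEs and carried-over events, overall and by antecedent treatment. Lifting the TEAE limit would match the scope already used for fatal events.
2. State in the SAP that a carried-over event with significant sustained worsening after the first open-label dose is a TEAE.
3. Cross-check the total against the disposition reason *Adverse event* and explain any differences.
4. Reconcile Table S-1, footnote i, with Protocol 7.3 on events arising between the antecedent end-of-treatment procedures and the first open-label dose.

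The cost is some wording and one changed table. Onset date and action taken are already collected. The discontinuation percentage may become slightly less favourable, and some of the added events will have begun on placebo, which the sub-rows by antecedent treatment make visible.

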14.2 Clinical Laboratory Variables

Clinical laboratory tests are performed at Baseline, Week 12, and Week 52 (EOT/ET).

In general, laboratory test results are from a central laboratory. Due to COVID-19 disruptions it is possible that some test results may be collected from a local laboratory. A separate eCRF will capture local laboratory results in order to facilitate medical monitoring of subject safety. Local laboratory results will not be included in any summary data analysis; they will, however, be included in separate data listings. All results (central and local) will be displayed in Système International [SI] units. It is encouraged, but not required, that clinical labs be completed under fasting conditions. The listings will include date and study day of collection. Out of range values will be flagged in the data listings.

- Hematology tests
 - Complete blood count (CBC) including:
 - White blood cell (WBC) count
 - Complete differential (relative and absolute)
 - Hematocrit (Hct), hemoglobin (Hgb), red blood cells (RBC), platelets
 - Reticulocyte count
- Clinical chemistry serum tests
 - Sodium (Na), potassium (K), chloride (Cl), phosphorus (P), calcium (Ca), carbon dioxide (CO₂), blood urea nitrogen (BUN), creatinine (Cr), uric acid
 - Alanine aminotransferase (ALT), aspartate aminotransferase (AST), gamma-glutamyl transpeptidase (GGT), alkaline phosphatase (ALP), total bilirubin (TBIL), lactate dehydrogenase (LDH)
 - Glucose
 - Albumin (ALB), total protein
 - Prolactin
 - Creatine kinase (CK)/creatinine phosphokinase (CPK)
 - Lipid panel
 - Total cholesterol, high-density lipoprotein (HDL)-cholesterol, triglycerides, low-density lipoprotein(LDL)-cholesterol, very low density lipoprotein cholesterol
- Urinalysis
 - Blood, RBCs, WBCs, protein, glucose, ketones, specific gravity, pH

Clinical laboratory values reported as continuous values for hematology, chemistry and urinalysis will be summarized using descriptive statistics at Baseline and scheduled post-Baseline visits. The change from Baseline values will also be summarized at scheduled post-Baseline visits. The overall minimum, maximum and last post-Baseline observed and change from Baseline values will also be summarized. For hemoglobin, hematocrit and uric acid, the above summaries will be presented for each gender as well as for both genders combined. For urinalysis with categorical results, the number and percentage of subjects will be tabulated by category at Baseline and scheduled post-Baseline visits, and the denominator is the number of subjects with non-missing values for the given parameter and visit. For glucose and lipid panel, the summary table will also be presented by fasting status (fasting vs. non-fasting).

Laboratory values will also be summarized in shift tables to determine the number and percentage of subjects with values classified as below (low), within (normal), or above (high) normal ranges at scheduled post-Baseline visits relative to the same classification at the Baseline visit. The shifts from Baseline to overall post-Baseline minimum and overall post-Baseline maximum will also be presented. For the by-visit shift summary, the denominator is the number of subjects with non-missing values at Baseline and the given visit for the given

parameter. For the summaries of shift from Baseline to the overall post-Baseline minimum or maximum, the denominator is the number of subjects with non-missing Baseline and at least 1 post-Baseline value for the given parameter. For hemoglobin, hematocrit and uric acid, the shift summaries will be presented for each gender as well as for both genders combined. For glucose and lipid panel, the shift table will be presented by fasting status (fasting vs. non-fasting).

Number and percentage of subjects with potentially clinically important (PCI) laboratory values at scheduled post-Baseline visits and overall post-Baseline will be summarized by Baseline status (all or within normal range) for selected parameters. PCI criteria are listed in [Table 2](#) and [Table 3](#). For the overall post-Baseline summaries, all post-Baseline values will be considered, including unscheduled and out of window values. Subjects with multiple PCI values for a given parameter will be counted only once for that parameter. For the by-visit summary, the numerator for the percentage is the number of subjects with a post-Baseline PCI value for the given parameter and visit, and the denominator is the number of subjects with non-missing values for the given parameter and visit. For the overall post-Baseline summary, the numerator for the percentage is the number of subjects with at least 1 post-Baseline PCI value for the given parameter, and the denominator is the number of subjects with at least 1 post-Baseline value for the given parameter. For hemoglobin, hematocrit, and uric acid, the count and percentage of subjects with PCI values will be presented for each gender as well as for both genders combined. A listing of all PCI values in study ACP-103-055 will be provided. This listing will include all observations from study ACP-103-055 for those subjects and parameters for which at least one PCI value (including OL Baseline) was observed.

Table 2 Criteria for Potentially Clinically Important Laboratory Values – Hematology and Chemistry

Analyte	Conventional Unit	Low PCI Criteria	High PCI Criteria	SI Unit	Low PCI Criteria	High PCI Criteria
Hematology (whole blood)						
Hemoglobin (male)	g/dL	<11	>18	g/L	<110	>180
Hemoglobin (female)	g/dL	<10	>17	g/L	<100	>170
Hematocrit (male)	%	<30	>55	L/L	<0.3	>0.55
Hematocrit (female)	%	<30	>50	L/L	<0.3	>0.5
Leukocyte (White Blood Cell Count)	x 10 ³ /uL	≤2.8	≥15	x 10 ⁹ /L	≤2.8	≥15
Neutrophils	x 10 ³ /uL	≤1.5	No upper limit	x 10 ⁹ /L	≤1.5	No upper limit
Platelet Count	x 10 ³ /uL	≤75	≥700	10 ⁹ /L	≤75	≥700
Chemistry (serum or plasma)						
ALT (SGPT)	U/L	No lower limit	≥3 X ULN	U/L	No lower limit	≥3 X ULN
AST (SGOT)	U/L	No lower limit	≥3 X ULN	U/L	No lower limit	≥3 X ULN
Total Bilirubin	mg/dL	No lower limit	≥1.5 ULN	umol/L	No lower limit	≥1.5 ULN
BUN	mg/dL	No lower limit	≥30.0	mmol/L	No lower limit	≥10.71
Creatine Kinase (CK)	U/L	No lower limit	≥3 ULN	U/L	No lower limit	≥3 ULN
Sodium	mEq/L	≤125	≥155	mmol/L	≤125	≥155
Potassium	mEq/L	≤3.0	≥5.5	mmol/L	≤3.0	≥5.5
Calcium, total	mg/dL	<8.0	>11.0	mmol/L	<2.0	>2.75
Lactate Dehydrogenase (LDH)	U/L	No lower limit	≥3 X ULN	U/L	No lower limit	≥3 X ULN
Alkaline Phosphatase	U/L	No lower limit	≥3 X ULN	U/L	No lower limit	≥3 X ULN
Uric acid (male)	mg/dL	No lower limit	≥10.5	umol/L	No lower limit	≥624.75
Uric acid (female)	mg/dL	No lower limit	≥8.5	umol/L	No lower limit	≥505.75
Albumin	g/dL	≤2.6	≥6.0	g/L	≤26	≥60
Total Protein	g/dL	≤5.0	≥10.0	g/L	≤50	≥100
Chloride	mEq/L	≤85	≥120	mmol/L	≤85	≥120
Glucose (random)	mg/dL	≤45.1	≥200.0	mmol/L	≤2.48	≥11
Serum Creatinine	mg/dL	Not Applicable	>1.5 ULN	umol/L	Not Applicable	>1.5 ULN
Triglycerides	mg/dL	Not Applicable	>300	mmol/L	Not Applicable	>3.39
Gamma-Glutamyl Transferase (GGT)	U/L	Not Applicable	≥3 ULN	U/L	Not Applicable	≥3 ULN

Table 3 Criteria for Potentially Clinically Important Laboratory Values - Urinalysis

Urinalysis (qualitative dipstick)	Low PCI Criteria	High PCI Criteria
Blood (occult blood)	Not Applicable	≥ Moderate
Protein	Not Applicable	≥ 100 mg/dL
Glucose	Not Applicable	≥ 500 mg/dL

The number and percentage of subjects with the shift from baseline, both double-blind and open-label, to weeks 12 and 52 that meet the following criteria in the blood lipid parameters and glucose will be summarized by fasting status (fasting vs. non-fasting):

- Total Cholesterol – (<200 mg/dL to ≥240 mg/dL)
- Triglycerides – (<150 mg/dL to ≥200 mg/dL)
- LDL Cholesterol – (<100 mg/dL to ≥160 mg/dL)
- HDL Cholesterol – (≥40 mg/dL to <40 mg/dL)
- Glucose fasting – (<100 mg/dL to ≥126 mg/dL)
- Glucose non-fasting – (<140 mg/dL to ≥140 mg/dL)
- Glucose fasting – (≥100 mg/dL and <126 mg/dL to ≥126 mg/dL)
- Glucose non-fasting - (≥140mg/dL and <200 mg/dL to ≥200 mg/dL)

The pregnancy results (positive or negative) for female subjects will be presented in a listing.

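### In SAP Table 2 the mg/dL and mmol/L limits for potentially clinically important random glucose differ by about 0.9%, and the SAP does not say which column sets the flag

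*SAP*

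**What the plan says.** Protocol Section 2.2.1 lists potentially clinically important laboratory values among the exploratory safety endpoints, and Protocol Section 9.5.2 leaves the criteria to the SAP. SAP Section 14.2 supplies them: "PCI criteria are listed in" Table 2 (hematology and chemistry) and Table 3 (urinalysis).

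Table 2 prints each limit twice, once in conventional and once in SI units. The row beginning "Glucose (random" reads ≤45.1 and ≥200.0 mg/dL, then ≤2.48 and ≥11 mmol/L.

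On units, the same section says: "All results (central and local) will be displayed in Système International [SI] units". It does not say which column of Table 2 is compared with the result when the flag is set.

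After Table 3, the section defines glucose and lipid shift categories in mg/dL only. One of them is "Glucose non-fasting - (≥140mg/dL and <200 mg/dL to ≥200 mg/dL".

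**The concern.** The two halves of a Table 2 row should be one criterion in two unit systems. For glucose they are not, and the gap is too large to be rounding: 45.1 mg/dL is about 2.50 mmol/L, which does not become 2.48 at the two decimals printed.

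The study is descriptive and plans no hypothesis tests (Protocol Section 9.2; SAP Section 5.1), so the PCI counts and percentages are themselves the reported result. The PCI listing also depends on the flag, because it covers only subjects and parameters with at least one PCI value. Two programmers who both follow the SAP, one using each column, could class the same borderline glucose differently.

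**Working it through.** **Inputs**
- Limits from SAP Table 2: ≤45.1 and ≥200.0 mg/dL; ≤2.48 and ≥11 mmol/L.
- Conversion factor: not in the documents. Assumed from the molar mass of glucose (C6H12O6): 6 × 12.011 + 12 × 1.008 + 6 × 15.999 = 180.156 g/mol. Then mmol/L = mg/dL × 10/180.156 = mg/dL × 0.055507.

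**Reproducing the printed SI limits.** The implied factors are 2.48/45.1 = 0.05499 and 11/200 = 0.05500. A single truncated factor of 0.055 gives both figures: 45.1 × 0.055 = 2.4805 and 200 × 0.055 = 11.00. The usual factors (0.0555, 1/18, 1/18.02) give neither.

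**Converting with the molar mass**

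| Limit | mg/dL printed | mmol/L equivalent | mmol/L printed | Difference | Printed SI limit in mg/dL |
|---|---|---|---|---|---|
| Low | 45.1 | 45.1 × 0.055507 = 2.503 | 2.48 | −0.93% | 2.48 × 18.0156 = 44.7 |
| High | 200.0 | 200 × 0.055507 = 11.10 | 11 | −0.91% | 11 × 18.0156 = 198.2 |

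Over factors from 1/18.02 to 1/18, the equivalents are 2.503 to 2.506 and 11.10 to 11.11 mmol/L. The back-conversions are 44.6 to 44.7 and 198.0 to 198.2 mg/dL. The choice of factor does not change the conclusion.

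**Other rows of Table 2 that need a molar conversion**

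| Analyte | Conventional | By molar mass (assumed) | SI printed | Difference |
|---|---|---|---|---|
| BUN | 30.0 | 30 × 10/28.014 = 10.709 | 10.71 | 0.01% |
| Uric acid, male | 10.5 | 10.5 × 10,000/168.11 = 624.59 | 624.75 | 0.03% |
| Uric acid, female | 8.5 | 8.5 × 10,000/168.11 = 505.62 | 505.75 | 0.03% |
| Triglycerides | 300 | 300 × 10/885.4 = 3.388 | 3.39 | 0.05% |
| Calcium, high | 11.0 | 11 × 10/40.078 = 2.745 | 2.75 | 0.2% |

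These rows agree within 0.2%. Glucose is the outlier.

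**Which values change class.** The columns disagree for glucose above 44.7 and up to 45.1 mg/dL, and from 198.2 to just under 200 mg/dL.
- In whole mg/dL these are 45 (2.498 mmol/L) and 199 (11.05 mmol/L). With the factor 1/18, 198 mg/dL also reaches the SI limit exactly (198/18 = 11.0).
- Low side in mmol/L: 2.49 (44.9 mg/dL) and 2.50 (45.0 mg/dL) are low by the mg/dL column and not by the SI column.
- High side in mmol/L: 11.0 (198.2 mg/dL) is high by the SI column and not by the mg/dL column. So are two-decimal values up to 11.09. A value of 11.1 back-converts to 199.97 mg/dL and is a rounding tie.

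The SI column therefore flags slightly fewer low values and slightly more high values.

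**The case against.** The strongest reply is that this hardly matters. The limits sort values in an exploratory, descriptive count. No test, stopping rule or dosing action is tied to Table 2, so they are not decision thresholds. Laboratory tests are scheduled only at Baseline, Week 12 and Week 52 or early termination, and the study stopped early with fewer subjects than planned (SAP Sections 3.5 and 3.6). About one whole-mg/dL value at each limit changes class, and all data are listed (SAP Section 5), so a borderline result remains visible. All of this stands and limits the point to a table correction.

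Three stronger readings are tempting, and the documents do not support them.
- A reader might infer that the SI column is the one actually applied, because results are displayed in SI. Display does not settle which column sets the flag. The shift criteria are in mg/dL only, so the SAP also classifies in conventional units, and the table specifications are in a separate document (SAP Section 1).
- A reader might infer that the SI figures are certainly the wrong ones. The low limit could have been converted in either direction: 2.48/0.055 = 45.09, so 45.1 may itself be a converted figure. For the high limit, the ≥200 mg/dL shift criterion supports 200 as the intended value.
- A reader might count the clash with the shift criterion as a second defect. It is the same mismatch seen again: the mg/dL limit in Table 2 agrees with the shift limit exactly, and only the SI entry departs from it. The shift analysis also requires a baseline category and is split by fasting status, so it is a different summary.

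**Conclusion.** The glucose row of Table 2 is internally inconsistent on both sides, by about 0.9% of each limit. The arithmetic is firm: it assumes only a standard conversion factor, and every usual factor gives the same answer. What cannot be settled from the documents is which column sets the flag and, for the low limit, which unit the threshold was first set in.

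Few or no subjects are likely to be reclassified. The documents contain no glucose data, so the shift in counts cannot be estimated. The primary endpoint, treatment-emergent adverse events, is unaffected. This is a minor correction, worth making because the row is wrong as written and costs almost nothing to put right.

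**What to change.** Reconcile the two glucose entries in SAP Table 2, and add one sentence to Section 14.2 saying which unit column drives the PCI flag for all analytes.

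If the mg/dL limits are the intended ones, change the SI entries to ≤2.50 and ≥11.1 mmol/L. With those entries, 45 mg/dL (2.498 mmol/L) is low in both columns, 199 mg/dL (11.05 mmol/L) is not high in either, and 200 mg/dL (11.10 mmol/L) is high in both. If the SI limits were the original ones, correct the mg/dL entries instead, to about 44.7 and 198.2, and explain why the high limit then differs from the 200 mg/dL shift criterion.

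The cost is two numbers and one sentence in the SAP, plus a check that the dataset specification uses the same limits. No new data are needed.
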